### **3 ELIGIBILITY CRITERIA**

#### **3.1 Inclusion Criteria**

1. Diagnosis of biopsy proven stage I-IIIB (cT1-3, N0-2a, M0) adenocarcinoma of the rectum; staging must also be based on multidisciplinary evaluation including MRI
2. Tumor  $\leq$  12 cm from anal verge as determined by MRI or endoscopy
3. Clinically detectable (MR, endoscopy, or DRE) tumor present
4. ECOG performance status 0-2
5. At least 18 years of age
6. Adequate bone marrow function defined as:
  - a. ANC  $>$  1,500 cells/mm^3
  - b. Hgb  $>$  8 g/dl
  - c. platelets  $>$  100,000 cells/mm^3
7. Women of childbearing potential and men must agree to use adequate contraception (hormonal or barrier method of birth control, abstinence) prior to study entry and for the duration of study participation. Should a woman become pregnant or suspect she is pregnant while participating in this study, she must inform her treating physician immediately.

8. Able to understand and willing to sign an IRB-approved written informed consent document.

### **3.2 Exclusion Criteria**

1. Prior radiation therapy, chemotherapy or extirpative surgery for rectal cancer.
2. Prior oxaliplatin or capecitabine use for any malignancy.
3. Prior radiation therapy to the pelvis.
4. A history of other malignancy (except non-melanomatous skin cancers) with the exception of malignancies for which all treatment was completed at least 2 years before registration and the patient has no evidence of disease.
5. Currently receiving any investigational agents.
6. A history of allergic reaction attributed to compounds of similar chemical or biologic composition to capecitabine, 5FU, oxaliplatin, or leucovorin.
7. Uncontrolled intercurrent illness including, but not limited to, ongoing or active infection, symptomatic congestive heart failure, unstable angina pectoris, or cardiac arrhythmia.
8. Pregnant and/or breastfeeding. Women of childbearing potential must have a negative serum pregnancy test within 14 days of study entry.
9. Patients with known history of HIV are eligible unless their CD4+ T-cell counts are < 350 cells/mcL or they have a history of AIDS-defining opportunistic infection within the 12 months prior to registration. Concurrent treatment with effective ART according to DHHS treatment guidelines is recommended. HIV testing for patients without a history of HIV is not a protocol requirement.

### **3.3 Inclusion of Women and Minorities**

Both men and women and members of all races and ethnic groups are eligible for this trial.

## **4 PATIENT REGISTRATION**

**Patients must not start any protocol intervention prior to registration through the Siteman Cancer Center.**

The following steps must be taken before registering patients to this study:

1. Confirmation of patient eligibility by Washington University
2. Registration of patient in the Siteman Cancer Center OnCore database
3. Assignment of unique patient number (UPN)

Once the patient has been entered in the Siteman Cancer Center OnCore database, the WUSM coordinator will forward verification of enrollment and the UPN via email.

### **4.1 Confirmation of Patient Eligibility**

Confirm patient eligibility by collecting the information listed below and scanning and emailing it to the research coordinator listed in the *Siteman Cancer Center Clinical Trials Core Protocol Procedures for Secondary Sites* packet at least one business day prior to registering patient:

1. Your name and contact information (telephone number, fax number, and email address)
2. Your site PI's name, the registering MD's name, and your institution name
3. Patient's race, sex, and DOB
4. Three letters (or two letters and a dash) for the patient's initials
5. Currently approved protocol version date
6. Copy of signed consent form (patient name may be blacked out)
7. Planned date of enrollment
8. Completed eligibility checklist, signed and dated by a member of the study team
9. Copy of appropriate source documentation confirming patient eligibility

#### **4.2 Patient Registration in the Siteman Cancer Center OnCore Database**

Registrations may be submitted Monday through Friday between 8am and 5pm CT. Urgent late afternoon or early morning enrollments should be planned in advance and coordinated with the Washington University research coordinator. Registration will be confirmed by the research coordinator or his/her delegate by email within one business day. Verification of eligibility and registration should be kept in the patient chart.

All patients at all sites must be registered through the Siteman Cancer Center OnCore database at Washington University.

#### **4.3 Assignment of UPN**

Each patient will be identified with a unique patient number (UPN) for this study. Patients will also be identified by first, middle, and last initials. If the patient has no middle initial, a dash will be used on the case report forms (CRFs). All data will be recorded with this identification number on the appropriate CRFs.

### **5 EVALUATION STUDIES**

#### **5.1 Pre-treatment**

Within 12 weeks of day of simulation for RT but no later than the first radiation treatment:

- Examination by treating surgeon, medical oncologist, and radiation oncologist
- CBC with diff, CMP, CEA
- Staging study to evaluate extent of disease in the chest, abdomen and pelvis: CT w/ contrast is preferred to rule out metastatic disease

- Rectal protocol MRI pelvis to assess the local extent of the primary tumor, including T and N stage.
- Pregnancy test (for women of childbearing potential) – within 14 days of first treatment
- Colonoscopy (within 6 months is acceptable)
  - If feasible it is strongly recommended that the following physical findings should be scored:
    - Tumor location (distance in cm from the anal verge to the distal tumor margin)
    - Circumferential lesion Y/N
- Research biopsy (see Section 11.1)
- Blood for ctDNA (see Section 11.2)
- FACT-C quality of life questionnaire

## 5.2 During Radiotherapy and Chemotherapy

Routine standard of care examinations and blood work will be done.

- CMP and CBC with differential prior to each cycle of chemotherapy
- On treatment assessment by radiation oncologist during the week of radiation therapy
- Assessment by medical oncology physician or nurse with each cycle of chemotherapy.
- Please see Section 6 for radiation therapy guidelines and Section 7 for chemotherapy guidelines.
- Rectal protocol MRI pelvis 8 weeks after completion of radiation (preferably after at least 3 cycles of chemotherapy completed) – OPTIONAL.

## 5.3 Completion of Chemotherapy/Post-Treatment Evaluation

Three to eight weeks after completion of chemotherapy, patients will have the following assessments:

- CEA
- FACT-C questionnaire.
- Surgical assessment w/ endoscopy (sigmoidoscopy preferred, rigid proctoscopy acceptable) to evaluate the extent of residual tumor
- Rectal protocol MRI pelvis to evaluate ycT and ycN stage
- Digital rectal exam (DRE) to evaluate ycT stage

For patients with a cCR, non-operative management will be pursued. For patients with residual disease who do not meet criteria for cCR by 3-8 weeks after completion of the last cycle of FOLFOX or CAPOX, further therapy is recommended and at the discretion of the treating physicians. At investigator discretion, patients who achieve a near clinical complete response with equivocal findings concerning for residual disease may be followed closely with short interval observation (i.e. 6-8 week MR/endoscopic follow-up),

with non-operative management pursued if a subsequent cCR is achieved. Patients whose disease is amenable to transanal endoscopic microexcision (TEM) or local excision (LE) may undergo TEM/LE to evaluate degree of residual disease. For those with ypT1 disease without LVSI present, non-operative management may continue with evaluation noted above. For those with residual ypT2-3 disease or ypT1 with LVSI, extirpative surgery including TME is recommended with treatment at investigators discretion proceeding off-study.

Post-treatment lymph nodes are to be evaluated by imaging and reviewed in multidisciplinary tumor board with a radiologist and classified as progressive, persistent disease, indeterminate or benign. Patients with progressive or persistent lymph node disease will not be eligible for non-operative management and will undergo additional therapy. Patients with indeterminate or benign lymph nodes AND cCR of primary will undergo non-operative management.

#### **5.4 Follow-up**

The FACT-C questionnaire and follow-up visit will be done 10-14 months from treatment (radiotherapy) start date.

Patients undergoing nonoperative management will be assessed for sustained cCR by rectal protocol MRI pelvis, endoscopy (sigmoidoscopy preferred, rigid proctoscopy accepted) and DRE every three months (not necessarily on the same day / appointment) for 1 year then every 3-4 months for the second year. If patient is unable to receive an MR pelvis every 3 months, every 6 months is acceptable as long as endoscopic exam is performed as per protocol schedule. CT chest and abdomen with contrast is to be obtained every 6 months for the first 2 years. Each of the follow-up studies and visits have a permitted variation of  $\pm 2$  weeks. After 2 years of follow-up on study, we recommend off-protocol follow-up with the same studies every 4-6 months per treating physician discretion.

Once a patient undergoes surgical resection they will undergo imaging and surgical follow-up as per institutional standard of care. These patients will continue to be followed for data collection for during study follow-up.

## **6 RADIATION THERAPY GUIDELINES**

### **6.1 Dose, Fractionation and Constraints**

When feasible it is strongly recommended that radiotherapy begin on a Monday. It is accepted that occasional logistical delays may occur during radiotherapy treatment due to machine downtime or other issues. Radiotherapy as administered during this study may take up to 10 business days without being considered a protocol deviation.

Radiotherapy will consist of five fractions, delivered once daily, to a total dose of 25 Gy at 5 Gy per fraction (PTV2500). An optional simultaneous integrated boost of 30 Gy in 5

fractions to the primary tumor is permitted. Monday through Friday treatment is strongly recommended. Daily imaging to verify accurate setup is mandatory. It is required that at least 95% of the PTV\_2500 receive at least 95% of the prescription dose and that the maximum dose be  $\leq$  115% of the prescription dose. Every effort should be made for 100% of the PTV\_2500 to be covered by 95% of the prescription dose. For treatment plans to 25 Gy, this is most reproducibly accomplished via a 3D plan with four fields and optional field-in-field technique. The maximum allowed dose to small bowel is 25 Gy (with an acceptable deviation of up to 25.5 Gy). A boost dose of 30 Gy in 5 fractions to the primary is strongly recommended for T3 tumors, tumors  $>4$  cm and tumors involving the circumferential resection margin.

It is recommended that pelvic lymph nodes outside of the mesorectum determined to be clinically suspicious by an experienced radiologist be boosted to 35 Gy in 5 fractions. The maximum allowed small bowel dose is 25 Gy (with an acceptable deviation of up to 25.5 Gy) when a primary or LN boost is given as well. There is no coverage requirement for boost doses. SIB plans may be delivered with IMRT (recommended) or multiple field 3D planning as long as dose constraints are met.

The following constraints are recommended (IMRT optimization) when boosting lymph node(s):

Bladder V20Gy  $<$  15 cc. Dmax  $<$  38 Gy.

Penile bulb V30Gy  $<$  3 cc.

Femoral heads V30Gy  $<$  10 cc.

Skin V36.5Gy  $<$  10 cc. Dmax  $<$  38.5 Gy.

## **6.2 Treatment Planning Procedures**

Image-based treatment planning and IMRT are permitted. Proton therapy is not permitted. Dose volume histogram (DVH) information for the target volumes, small bowel, and uninvolved colon (defined to be large bowel outside the clinical target volumes) is mandatory. This is to assist in interpreting outcome, including morbidity. Daily cone beam CT to assess for rectal and bladder filling is recommended.

## **6.3 Simulation Procedures/Patient Positioning**

The prone position with a bowel displacement device incorporated into the immobilization cast is generally recommended as the best way to exclude small bowel from the pelvis. The exceptions would be patients unable to lay prone or morbidly obese patients whose diagnostic supine CT scans demonstrate little or no small bowel in the pelvis. Those patients with good bladder control should be treated with a full bladder per institutional practice to further exclude small bowel. All patients should be simulated with oral small bowel contrast.

## **6.4 Clinical Target Volume (CTV) and Planning Target Volume (PTV) Definitions and Radiation Treatment Planning**

Contouring should be as per the RTOG anorectal contouring atlas. CTV\_2500 should include rectum and associated mesentery extending caudad at least to two cm below the distal edge of palpable disease. Superiorly it should include the rectum and its mesentery to the level of the rectosigmoid or two cm proximal to macroscopic disease, whichever is more cephalad. In addition, the internal iliac, internal obturator, and pre-sacral lymph node regions should be included (superiorly to approximately the level of L5/S1, including the inferior mesenteric vessels). PTV\_2500 is generated by a uniform 0.5-0.7 cm expansion about CTV\_2500. CTV\_3000 for boost is 0.5 cm expansion off of the GTV. PTV\_3000 is a 0.5-0.7 expansion off of CTV\_3000. If a SIB for extra-mesorectal pelvic lymph nodes is used, CTV\_3500 should be a 0.5 cm expansion from the gross lymph node. PTV\_3500 is a 0.5-0.7 cm expansion from CTV\_3500.

It is required that a physician review daily setup images (either pre or post-treatment) for each of the five fractions.

Ideally the 95% dose should not extend more than 3-6 mm below or above the PTV contour.

## 6.5 Normal Tissue Contours

Individual loops of small bowel should be contoured tightly. Bowel bag is not permitted. The CTV is NOT to be extracted from small bowel. If small bowel lies within a CTV, that WILL contribute to the small bowel dose. Since absolute rather than relative bowel volumes are to be tracked, it is not necessary to contour the entire small bowel, only those loops caudal to 2 cm above the most cephalad extent of PTV\_2500.

# 7 CHEMOTHERAPY GUIDELINES

## 7.1 Chemotherapy Schedule and Doses

Chemotherapy should begin 2 to 4 weeks after completion of radiotherapy and will consist of FOLFOX (5FU/leucovorin/oxaliplatin) every other week for 8 courses (16 weeks). Leucovorin may be substituted with levoleucovorin (200 mg/m^2) if leucovorin is not available. Alternatively, CAPOX (capecitabine/oxaliplatin) may be given for 5 cycles over 15 weeks. A maximum (total) delay of treatment of 4 weeks is allowed per protocol due to factors or adverse events (AEs) listed in this section. Cumulative delays in excess of 4 weeks will need to be discussed with the Principal Investigator. Such cases will need to be individualized depending on the clinical scenario. Patients receiving CAPOX will be given a pill diary (Appendix B) to assess compliance for capecitabine.

## 7.2 Agent Administration

FOLFOX			
Agent	Dose	Route	Schedule
Oxaliplatin*	85 mg/m 	IV over 2 hours	On Day 1, Q 14 days

Leucovorin*	400 mg/m 	IV over 2 hours	On Day 1, Q 14 days
5-FU Bolus*	400 mg/m 	IV push	On Day 1, Q 14 days
5-FU Infusion*	2400 mg/m 	IV CIIIV	On Day 1, Q 14 days over 46 hours

\*Administer sequentially as written, except oxaliplatin and leucovorin may be administered concurrently

CAPOX			
Agent	Dose	Route	Schedule
Capecitabine	1000 mg/m 	PO	BID Days 1-14, Q21 days
Oxaliplatin	130 mg/m 	IV over 2 hours	On Day 1, Q 21 days

Dose calculations for both regimens should be based on actual weight and not corrected for obesity.

### 7.3 Supportive Care Recommendations

Veno-occlusive disease is a very rare AE associated with the administration of the combination of 5-FU and oxaliplatin. VOD disease is characterized by hepatomegaly, ascites, and jaundice. These signs and symptoms should prompt consideration of VOD. A Doppler ultrasound showing reversal of portal blood flow or other evidence of portal hypertension is suggestive of this diagnosis. In addition, standard clinical practice for evaluation of VOD should include observation of liver and spleen size, history of or gastrointestinal bleeding, development of esophageal varices, ascites, bleeding, or jaundice. All patients on and off therapy who develop signs and symptoms suggestive of VOD should be thoroughly evaluated and closely monitored and supported as clinically dictated.

Grade 3/4 hypersensitivity, including anaphylactic/anaphylactoid reactions, has been observed with oxaliplatin. These allergic reactions, which can be fatal, can occur within minutes of administration, and can occur during any cycle. There were similar in nature and severity to those reported with other platinum-containing compounds, such as rash, urticaria, erythema, pruritus, and rarely bronchospasm and hypotension. These reactions are usually managed with standard epinephrine, corticosteroid, and antihistamine therapy, and require discontinuation of therapy.

Ice should be avoided during the infusion of oxaliplatin because cold temperatures can exacerbate acute neurological symptoms.

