## 8.3 Dose Modifications for Toxicity Related to FOLFOX-6

Dose modifications during FOLFOX chemotherapy are at the discretion of the primary treating provider. The use of 5-FU bolus is at the discretion of the treating physician. Modifications should be reported to research coordinator. Refer to the tables below for guidance regarding suggested dose reductions and treatment delays, consistent with best oncologic practices.

Toxicity NCI Grade (Value)	Worst interval toxicity	Day of treatment	
Neutropenia (ANC)			
Grade 1 (ANC < LLN – 1500/mm  )	Maintain dose level	If ANC < 1000 on day of treatment, hold and check weekly until $\geq$ 1000 mm  . Then treat based on interval toxicity. If ANC < 1000 after 4 weeks, discontinue therapy.	
Grade 2 (ANC < 1499 – 1000/mm  )			
Grade 3 (ANC < 999 – 500/mm  )			
Grade 4 (ANC < 500/mm  )	Reduce 1 dose level		
Thrombocytopenia			
Grade 1 (PLT < LLN – 75,000/mm  )		If PLT < 75,000 on day of treatment, hold and check weekly until $\geq$ 75,000 mm  . Then treat based on interval toxicity. If PLT < 75,000 after 4 weeks, discontinue therapy.	
Grade 2 (PLT 74,999 – 50,000/mm  )			
Grade 3 (PLT 49,999 – 25,000/mm  )			

Grade 4 (PLT< 25,000/mm  )		
Diarrhea		
Grade 1	Maintain dose level	
Grade 2	Reduce 5-FU and oxaliplatin 1 dose level	
Grade 3		
Grade 4		Hold chemotherapy if any grade of diarrhea above grade 1 is present with the patient not taking antidiarrheal agents within 24 hours of treatment. Reduce 5-FU and oxaliplatin 1 dose level upon resolution of diarrhea. If diarrhea has not resolved within 4 weeks of scheduled treatment day, discontinue therapy.
Other nonhematologic toxicities (except neurologic, alopecia, anorexia, nausea/vomiting if can be controlled by antiemetics)		
Grade 1	Maintain dose level	Maintain dose level
Grade 2		
Grade 3	Reduce 1 dose level	Hold until resolved to grade $\leq 1$ . Reduce 5-FU and oxaliplatin 1 dose level
Grade 4		

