## **12 PHARMACEUTICAL INFORMATION**

FOLFOX and CAPOX are standard of care, FDA-approved regimen for the treatment of rectal cancer, and treatment will be provided and administered according to standard of care guidelines. More detailed information can be found in the products' package inserts.

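### Minor safety inconsistency (FOLFOX only): 7.3 calls for discontinuation after grade 3/4 oxaliplatin hypersensitivity, but the suggested dose table in 8.3 leaves it in a row whose grade 3 action is a one-level reduction

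*Combined protocol and SAP*

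**What the plan says.** Section 7.3 (Supportive Care Recommendations) introduces the event: "Grade 3/4 hypersensitivity, including anaphylactic/anaphylactoid reactions, has been observed with oxaliplatin". It adds that these reactions can be fatal, can begin within minutes of administration and can occur in any cycle. On management it says: "These reactions are usually managed with standard epinephrine, corticosteroid, and antihistamine therapy, and require discontinuation of therapy".

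Section 8.3 gives the FOLFOX dose-modification table. Its last row is a residual category: "Other nonhematologic toxicities (except neurologic, alopecia, anorexia, nausea/vomiting if can be controlled by antiemetics"). At grade 3 the column for worst interval toxicity reads "Reduce 1 dose level". The day-of-treatment column begins "Hold until resolved to grade" 1 or lower, and then reduces 5-FU and oxaliplatin by one level.

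The same section limits the force of its table: "Dose modifications during FOLFOX chemotherapy are at the discretion of the primary treating provider", and "Refer to the tables below for guidance regarding suggested dose reductions and treatment delays, consistent with best oncologic practices".

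Section 8.2 sets the FOLFOX oxaliplatin levels at 85, 65, 50 and 40 mg/m². It lets the drugs be modified independently, and it lets a patient who cannot tolerate one drug stay on study with the rest. Section 12 says of both regimens that "treatment will be provided and administered according to standard of care guidelines", and refers to the package inserts for detail.

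**The concern.** Hypersensitivity is a nonhematologic toxicity. It has no row of its own in 8.3 and is not among the residual row's exceptions, so on a literal reading that row covers it. A clinician who looks up the next dose in the dose-modification section after a grade 3 reaction finds an instruction to reduce. The instruction to stop is under supportive care, and neither section refers to the other.

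What is at stake is patient safety: re-exposure to oxaliplatin at a reduced dose after a severe allergic reaction. No inferential property of the trial is involved.

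**Working it through.** No figure in the plan needs reproducing, and the only arithmetic is the dose step. The check sets the sections side by side.

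**1. Does any other row or section take hypersensitivity out of the residual row?**
- The other rows of 8.3 cover neutropenia, thrombocytopenia and diarrhea.
- The residual row's exceptions are neurologic toxicity, alopecia, anorexia, and nausea or vomiting that antiemetics can control.
- Section 8.4 covers only paresthesia and dysesthesia.
- Exclusion 6 in 3.2 bars patients with a history of allergy to compounds similar to the study drugs. It is an entry rule and does not govern reactions on study.

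So nothing in the dose-modification text removes hypersensitivity from the residual row.

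**2. What does each section direct at grade 3?**

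| Source | Situation | Action | Oxaliplatin from the starting dose |
|---|---|---|---|
| 8.3, interval column | Reaction resolved by the next treatment day | Reduce one level | 85 to 65 mg/m² |
| 8.3, day-of-treatment column | Reaction still present | Hold to grade 1 or lower, then reduce one level | 85 to 65 mg/m² |
| 7.3 | Grade 3/4 reaction | Discontinue therapy | None, on the natural reading (assumption) |

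The step is 85 − 65 = 20 mg/m², or 20/85 = 23.5% of the starting dose. The interval cell names no drug and is read here as including oxaliplatin. The day-of-treatment cell names 5-FU and oxaliplatin.

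**3. Is silence in the row likely to be read as permission to continue?** Elsewhere the tables say so when treatment should end. Section 8.3 stops therapy for neutropenia, thrombocytopenia or diarrhea not resolved after 4 weeks, and 8.4 stops oxaliplatin for the worst neurotoxicity. A row that only reduces can therefore be taken to mean continue at the lower dose. Section 8.2 also permits re-escalation after a toxicity reduction at the physician's discretion, and does not except hypersensitivity.

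**4. How far does it extend?**
- *CAPOX:* 8.5 defers to package inserts and standard practice, and its only table is for diarrhea due to capecitabine. It has no comparable residual row.
- *Grade 4:* those cells of the 8.3 row are blank in the text available for review and may be merged with grade 3. No conclusion is drawn for grade 4 under 8.3.
- *Frequency:* the documents give no reaction rate, so no number of patients can be estimated.

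**The case against.** The strongest reply is that there may be no contradiction. Section 7.3 does not say which therapy is discontinued or for how long. The sentence describes acute management of a reaction that can begin within minutes, so it could mean only that the infusion is stopped. On that reading 7.3 covers the acute event and 8.3 covers later dosing. This stands in part. No further oxaliplatin is the more natural reading, but it is an inference, and the contrast with 65 mg/m² depends on it. It also means that 7.3 itself needs clarifying.

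The second reply is that the documents already handle the event. Section 7.3 addresses this drug and grade directly, while 8.3 offers a general row in a suggested, discretionary table, and Section 12 places treatment under standard of care. A specific instruction ordinarily prevails over a general one. This also stands, and it is why the point is minor. It does not reconcile the two texts: the protocol gives no rule of precedence between them, and 8.3 presents its table as consistent with best practice.

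The third reply is that the day-of-treatment cell will seldom apply, because a reaction that begins within minutes is unlikely to persist to the next treatment day. That is reasonable, but the interval cell covers the resolved reaction and leads to the same reduction.

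**Conclusion.** The inconsistency is real and minor. For grade 3 hypersensitivity on FOLFOX, the literal 8.3 action from the starting dose is oxaliplatin at 65 instead of 85 mg/m². Section 7.3 calls for discontinuation. The conclusion rests on two assumptions: that discontinuation in 7.3 means no further oxaliplatin, and that the interval cell in 8.3 includes oxaliplatin.

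A reader might infer that the protocol requires rechallenge after a severe allergic reaction. The documents do not support that, because 8.3 is guidance under provider discretion and 7.3 points the other way. Nor do they support extending the point to CAPOX, making any claim about grade 4 under 8.3, or describing 7.3 as expressly requiring permanent cessation of oxaliplatin. Sample size, error rates, power and the planned analyses are not affected.

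**What to change.** Make two changes together.

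1. In 8.3, add hypersensitivity to the exceptions of the residual row, with the line: *grade 3/4 hypersensitivity: discontinue oxaliplatin, see 7.3*.
2. In 7.3, amend the closing words on these reactions to: *require permanent discontinuation of oxaliplatin*, and note that the other drugs may continue under 8.2.

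The second change is needed because the new cross-reference would otherwise lead to text that does not state the rule. If the sponsor intends something narrower than permanent discontinuation, 7.3 should say so and the 8.3 line should match it.

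The cost is a phrase in one table row and a phrase in one sentence, which can go into the next amendment. Schedule, sample size and analysis do not change.
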